Specific Aims and Hypothesis, Phase I

Specific Aim #1: To assess feasibility of measuring TV in the DR for preterm infants <32 weeks with need for invasive positive pressure ventilation via endotracheal tube (ETT).

Hypothesis 1: We hypothesize that measurement of TV in intubated preterm infants <32 weeks in the DR is feasible.

Specific Aim #2: To assess variability in delivered TV in the DR with PLV for preterm infants <32 weeks with need for invasive positive pressure ventilation via ETT.

Hypothesis 2: We hypothesize that the TV generated via PLV in the immediate neonatal transition phase will be highly variable.

Specific Aims and Hypothesis, Phase II

Specific Aim #1: To assess feasibility of providing VTV, by quickly adjusting the peak inspiratory pressures (PiP) provided via the T-Piece resuscitator based on real time TV measurements.

Hypothesis 1: We hypothesize that real time PiP adjustments are feasible when utilizing a T-Piece resuscitator to provide VTV for goal TV of 4-6ml/kg.

Specific Aims #2: To compare the pulmonary mechanics and physiology during VTV, respiratory support requirements for infants receiving VTV versus PLV.

Hypothesis 2: We hypothesize that infants receiving VTV will require lower PiP, will have lower oxygen needs

Specific Aim #3: To assess complication rates and long term outcomes for infants receiving VTV versus PLV

Hypothesis 3: We hypothesize that VTV in the DR will have similar complication rates as compared to PLV with improved long term pulmonary morbidities..

Outcome and Implications: Successful pilot study will demonstrate that for preterm infants <32 weeks VTV in DR is feasible and safe; provides consistent measurable TV with lower PiP and decreased oxygen needs as compared to PLV. Data from this pilot study would then serve as a basis for a future RCT comparing the role of VTV with PLV in DR resuscitation and their impact pulmonary outcomes for preterm infants.

STATEMENT OF PURPOSE

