Despite significant improvement in preterm infant survival, the incidence of bronchopulmonary dysplasia (BPD) in infants born ≤ 28 weeks gestational age (GA) has been relatively stable at $\sim 40\%$ ^{i,ii,iii}, with 10,000–15,000 new cases estimated annually^{iv}. Delivery room (DR) management of preterm infants during the initial resuscitation has a significant impact on future development of BPD. Current DR practice as recommended by the Neonatal Resuscitation Program (NRP), focuses on providing positive pressure ventilation (PPV) for intubated infants based on pressure limited ventilation (PLV). But with rapidly changing pulmonary compliance during the early newborn period, PLV may lead to under or over inflation of the lungs and induce significant volutrauma, barotrauma and/or atelactetrauma, all of which are associated in the pathogenesis of BPD. No studies have specifically reported tidal volume (TV) provided in the DR in intubated infants with current PLV practices. Similarly, no study has evaluated the safety and efficacy of volume targeted ventilation (VTV) in the DR and its impact on BPD.

With the proposed study, in Phase I, we aim to demonstrate that measuring TV in intubated infants receiving PPV via PLV is feasible. We also seek to demonstrate that with PLV, TV is highly variable in the first few hours of life, even with the same peak inspiratory pressures (PiP) due to rapidly changing pulmonary compliance. A successful Phase I will demonstrate that measuring TV is feasible in the DR, and with information on real time actual TV achieved during PPV, it is possible to target the TV for a goal TV by adjusting the PiP provided.

Phase II will be a pilot randomized control trial to demonstrate feasibility of VTV compared to PLV. We will also aim to understand the pulmonary mechanics and physiology during VTV. A successful Phase II will demonstrate VTV is feasible, is associated with stable TV, decreased peak inspiratory pressure and oxygen needs compared to PLV, and not associated with increased complications compared to PLV. It will thereby justify a larger randomized control trial with enough power to evaluate the efficacy of VTV in reducing BPD and other long term pulmonary morbidities for preterm infants.

[figure not shown]
BACKGROUND

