Phase II: We will enroll a total of 30 patients (15 per study group). The sample size was selected to insure sufficient number of patients to estimate variability and effect sizes^{xxi} and to estimate recruitment rates. For example, with 30 patients, the width of the 95% confidence will be about 55% as wide as the standard deviation. This estimate will help develop sample size estimates for future studies.

DATA COLLECTION AND STORAGE

Study data will be collected and managed using a secure, web-based, password protected RedCap (Research Electronic Data Capture) data base^{xxii}. Baseline demographic maternal and infant characteristics, TV, PiP, mean airway pressure, PEEP, FiO₂, resuscitation details, duration of invasive mechanical ventilation, duration of non-invasive respiratory support (non-invasive mechanical ventilation, continuous positive airway pressure), duration of oxygen treatment, home O₂ requirement, BPD incidence and severity along with pulmonary complications will be collected. Standard BPD definition of mild (oxygen use for 28 days), moderate (oxygen need at 36 weeks), or severe (ventilatory support at 36 weeks), along with physiologic BPD testing at 36 weeks will be used to define BPD. This data will also be used prospectively in a future randomized control trial if feasibility study is successful. The research team members and DSMB will have access to the full data set.

DATA ANALYSIS

As the study is designed as a pilot, no formal tests of hypotheses will be conducted^{xxiii}. In Phase I, our goal is to attain skill and competency with using the device, as well as to establish that our measures are reliable and valid. Descriptive statistics will be use to assess the feasibility of measuring TV in the DR. Feasible will be defined as being able to successfully measure the TV in 80% of the infants within 60 seconds of starting PPV via the endotracheal tube.

For Phase II of the pilot project, data analysis will be limited to point estimates (e.g., means and proportions). We will describe the feasibility of using VTV in the DR, and data analysis will be limited to estimating the point estimates (e.g., means and proportions) and variability of ventilatory measures in each group and overall. We will also estimate recruitment and attrition rates, as well as the duration of the consenting process.

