We will use the pilot phase to begin identifying and assessing the frequency of adverse events for developing safety measures. Additionally, the pilot data will be used to estimate effect sizes and variability so that sample size and statistical power may be computed for a later randomized control trial.

Although this study will not be powered to evaluate differences in longer term pulmonary outcomes like BPD, we will still assess for possible trends in difference of BPD and other pulmonary outcomes between the two groups. Being a feasibility study, this study will not be powered to evaluate the safety and other long term outcomes between the two arms, but we will collect and analyze the safety data especially since we will be using the enrolled patient data for the future randomized control trial.

VULNERABLE POPULATION

This study involves studying newborn infants, who are considered vulnerable population. In phase I, the subjects involved in the study will have minimal risks as they will receive standard of care practices and we will only assess our ability to measure the TV in this population. In Phase II, the control arm has minimal risk as they will receive standard of care practices. The intervention arm may potentially have direct benefit as with the information about TV during resuscitation, we can target our PiP for goal TV, thereby minimizing volutrauma and/or atelectotrauma. Thus, overall this study poses none to minimal risk for the study subjects and may potentially benefit the infants in the intervention arm.

For the Phase II the study related interventions will be done only after a written informed parental consent has been obtained.

DATA AND SAFETY MONITORING

Safety data will be monitored closely for all enrolled subjects with special focus on infants randomized to the intervention arm in Phase II. Subjects in the intervention arm, based on the tidal volume generated, the maximum PiP will be limited at 30cm of H₂O, as it would be considered unconventional to require more PiP than 30cm of water in the immediate neonatal phase for longer than 60 seconds duration. If the tidal volume cannot be measure within 60 second, the patients will continue to receive conventional PLV during the time eliminating any potential harm to the patient. We will monitor for development of any pulmonary complication in the enrolled subjects including but not limited to pneumothorax, pneumo-mediastinum, and pulmonary interstitial emphysema.

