Low intubation rates in the DR and low enrollment rate: With the increased usage of noninvasive respiratory support, the number of intubated infants in the DR might be lower than anticipated. In that situation, we are open to making this study a multicenter feasibility study with University of Massachusetts Medical School-Worcester as a potential partner. Additionally, for Phase I, we can also evaluate the feasibility of measuring TV in infants undergoing “INSURE” (intubation, surfactant and rapid extubation) for respiratory distress syndrome, as these infants also tend to be premature <32 weeks infants with rapidly changing pulmonary compliance after administration of surfactant therapy.

ANTICIPATED RESULTS AND IMPACT

Phase I: Tidal volume can be rapidly measured in more than 80% of intubated infants in the DR. TV is highly variable in the immediate newborn period, which can result in significant over or underdistension of the lungs, predisposing the infant to lung injury from volutrauma and/or atelectotrauma. A successful Phase I study will demonstrate the potential that a goal TV can be targeted during PPV by adjusting the PiP provided.

Phase II: We anticipate demonstrating that delivering VTV in DR is feasible for optimal lung recruitment; which when continued in the NICU may potentially reduce lung injury as well as long-term pulmonary complications including BPD. The study will provide evidence and pilot data to support the need for a larger, multi-center randomized control trial comparing VTV versus PLV during DR neonatal resuscitation. It will also provide evidence supporting the lung protective impact of VTV, and can potentially lead to significant change in practices from pressure limited to volume targeted respiratory support during neonatal resuscitation.

PUBLICATION PLANS

The results from the study will presented in various local, regional and national conferences, with the eventual goal of publishing the results in a peer review journal.

REFERENCES

ⁱ Zysman-Colman Z., Tremblay G.M., Bandeali S., Landry J.S. Bronchopulmonary dysplasia—trends over three decades. *Pediatr. Child Health.* 2013;18:86–90

ⁱⁱ Day C.L., Ryan R.M. Bronchopulmonary dysplasia: Old becomes new again! *Pediatr. Res.* 2016 doi: 10.1038/pr.2016.201.

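### Phase II is said to demonstrate that VTV is safe and has no excess of complications, but 15 infants per arm analysed descriptively cannot show this, and no rule covers deaths before BPD is graded

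*Combined protocol and SAP*

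**What the plan says.** Under Specific Aims and Hypothesis, the Outcome and Implications paragraph states: "Successful pilot study will demonstrate that for preterm infants <32 weeks VTV in DR is feasible and safe". It adds consistent tidal volume (TV), lower peak inspiratory pressure (PiP) and lower oxygen need. The Statement of Purpose lists much the same conditions for a successful Phase II and ends "and not associated with increased complications compared to PLV. It will thereby justify a larger randomized control trial". Innovation repeats the pressure and oxygen claim. Anticipated Results and Impact adds that the study will give "evidence supporting the lung protective impact of VTV".

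Data Analysis is more cautious:

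- "As the study is designed as a pilot, no formal tests of hypotheses will be conducted".
- Phase II analysis is confined to "estimating the point estimates (e.g., means and proportions) and variability of ventilatory measures in each group and overall".
- Later, "the pilot data will be used to estimate effect sizes and variability", to plan the next trial.
- On safety, "this study will not be powered to evaluate the safety and other long term outcomes between the two arms".
- On BPD, "we will still assess for possible trends in difference of BPD and other pulmonary outcomes between the two groups".

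Sample Size sets 30 infants, 15 per arm. Primary Outcome Variable gives the Phase II outcome as similar timing of initiation for VTV and PLV. The 80% feasibility threshold in Data Analysis is stated for Phase I only.

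The Phase II objectives name pneumothorax, unexpected adverse events, ventilation duration, BPD and home oxygen. Data Collection and Storage grades BPD by support at 28 days and 36 weeks. Neither place names death.

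**The concern.** The purpose text promises a conclusion that the analysis text disclaims. Absence of excess complications is one of the conditions offered as justification for the larger trial. If few events occur, or the counts are equal, a reader could take that condition as met although the data would also fit a sizeable excess under VTV.

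BPD raises a related problem. It is graded at 36 weeks, so an infant who dies earlier has no grade. Without a stated rule, the same data give different BPD rates by arm. The protocol intends to use Phase II data for effect sizes and to carry them into the later trial, so the unstated choice would carry forward too.

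**Working it through.** **Inputs.** The 15 per arm comes from Sample Size and the 1:1 allocation from Randomization. The protocol gives no complication rate, SD, expected difference, margin or significance level. The 95% two-sided intervals and 5% two-sided tests below are my convention, for illustration.

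**1. The plan's own precision figure.** Sample Size says that with 30 patients the 95% interval is about 55% as wide as the SD. The chi-square interval for an SD at n = 30 runs from √(29/45.72) = 0.796 to √(29/16.05) = 1.344 SD, a width of 0.548. The figure therefore reproduces as the precision of a variability estimate. It says nothing about complication rates.

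**2. No events in one arm.** The exact (Clopper-Pearson) upper limit for 0/15 is 1 − 0.025^(1/15) = 0.218, or 21.8%.

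**3. Equal counts in both arms.** I used the Newcombe interval for a difference, built from the Wilson limits l and u of each arm. With equal counts and p = x/15, the half-width is √[(p − l)² + (u − p)²].

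| Events, VTV vs PLV | Wilson limits per arm | 95% CI for the difference |
|---|---|---|
| 0/15 vs 0/15 | 0 to 0.204 | ±20.4 points |
| 1/15 vs 1/15 | 0.012 to 0.298 | ±23.8 points |
| 2/15 vs 2/15 | 0.037 to 0.379 | ±26.4 points |

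**4. How often a real excess would go unseen.** Suppose VTV truly doubled the complication rate. With independent Binomial(15) counts, the chance that the VTV count is no higher than the PLV count is:

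- 44% for 5% vs 10%
- 30% for 10% vs 20%
- 22% for 15% vs 30%
- 15% for 20% vs 40%

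All these rates are assumptions.

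**5. Pressure and oxygen.** The 95% half-width for a difference in means is t(28; 0.975) × √(2/15) = 2.048 × 0.365 = 0.75 SD. The power of a two-sample t-test with 15 per arm is 26% at 0.5 SD, 51% at 0.75 SD, 75% at 1.0 SD and 80% at 1.06 SD.

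**6. Deaths and the BPD rate.** The counts here are invented to show the mechanism. Take 5 BPD cases in an arm of 15.

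| Deaths before 36 weeks | Deaths counted as no BPD | BPD among survivors | Death or BPD |
|---|---|---|---|
| 1 | 5/15 = 33% | 5/14 = 36% | 6/15 = 40% |
| 3 | 5/15 = 33% | 5/12 = 42% | 8/15 = 53% |

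The protocol does not say which column it would report.

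**The case against.** The strongest reply is that the operative section is already right. Data Analysis rules out formal tests, says safety is not powered and treats BPD as a matter of possible trends. The overstatement sits in purpose and impact text. This stands as far as the planned analysis goes, and it is why the safety remedy is mainly rewording. It does not remove the conflict, because the overstated sentence is also the stated justification for the next trial.

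Five stronger readings are tempting, and the documents do not support them.

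- **The sample is too small.** A descriptive pilot of 30 is legitimate, and its precision figure reproduces.
- **Equal or zero complication counts would trigger the larger trial.** The Statement of Purpose lists several conditions together and sets no go/no-go rule on counts.
- **A pressure or oxygen difference below 1 SD could not be shown.** Power is 51% at 0.75 SD, and 1.06 SD is only where it reaches 80%. No such test is planned in any case.
- **Deaths would go unrecorded.** They may be captured as serious adverse events or within the safety data, and by-arm safety reporting is implied by Aim #3. The gap is that death is not named and has no rule in the BPD outcome.
- **Phase II has no success criterion.** It has a primary outcome, the timing of initiation, although no threshold for similarity is given.

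The complication hypothesis is similar rates in Specific Aims and Hypothesis but lower rates in the later Hypothesis section. This is a real inconsistency, but a minor one because neither version will be tested.

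**Conclusion.** The concern holds in a limited form. With 15 per arm and descriptive analysis, Phase II cannot demonstrate that VTV is safe or free of excess complications. Even the most favourable equal result, no events in either arm, leaves about ±20 percentage points open, and two events in each arm leaves about ±26. These intervals depend only on the planned sample size and the 95% level. The doubling scenarios and death counts rest on assumed figures and only illustrate the point.

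Lower PiP or oxygen need would be shown reliably only for a true difference of about 1 SD. The lung-protection claim goes beyond the possible trends that the analysis section allows. BPD by arm depends on an unstated choice about infants who die before 36 weeks. These points should be corrected, but they do not undermine the pilot as a feasibility study.

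**What to change.** 1. In Outcome and Implications and the Statement of Purpose, limit the Phase II success claim to feasibility. Tie it to the stated primary outcome and say what counts as similar timing.
2. In those two places, and in Innovation and Anticipated Results and Impact, describe safety, PiP, oxygen and lung-protection results as descriptive estimates, in line with Data Analysis.
3. In Data Analysis, report complications by arm with exact 95% CIs. Give between-arm differences in complications, PiP and FiO2 with 95% CIs. This builds on the effect-size estimates already planned.
4. Add death before 36 weeks and death before discharge to the data list. Report death by arm, and death or BPD among all randomised infants beside BPD among survivors.
5. As a minor edit, state the same complication hypothesis in both places.

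The cost is some rewording, one routinely available data item and a few interval estimates, with no change in sample size. The claims become more modest and the intervals will be wide.

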Secondary Hypothesis: We hypothesize that the TV generated via PLV in the immediate neonatal transition phase will be highly variable.

PHASE II:

Primary Hypothesis: We hypothesize that real time PiP adjustments are feasible when utilizing a T-Piece resuscitator to provide VTV for goal TV of 4-6ml/kg that can be seamlessly transitioned in the NICU.

Secondary Hypothesis:

- i. We hypothesize that infants receiving VTV will require lower PiP, will have lower oxygen needs with improved long term pulmonary morbidities
- ii. We hypothesize that VTV will have lower complication rates as compared to PLV.

SPECIFIC AIMS:

PHASE I:

Specific Aim #1: To assess feasibility of measuring TV in the DR for preterm infants <32 weeks with need for invasive positive pressure ventilation via endotracheal tube (ETT).

Objectives:

Date 10/15/2018
Protocol Version-I

- To assess the % infants with all equipment ready(including NM3 monitor and flow sensor) in DR to measure TV
- To assess the % infants where TV was measured within 60 seconds of ETT placement and positive pressure ventilation initiation.

Specific Aim #2: To assess variability in delivered TV in the DR with PLV for preterm infants <32 weeks with need for invasive positive pressure ventilation via ETT

Objectives:

- To assess the % infants with tidal within goal of 4-6ml/kg via routine PLV
- To assess the % infants with under or over ventilation using routine PLV
- To assess changes in TV with administration of surfactant with the same pressures

PHASE II:

Specific Aim #1: To assess feasibility of providing VTV, by quickly adjusting the peak inspiratory pressures (PiP) provided via the T-Piece resuscitator based on real time TV measurements.

Objectives:

- To assess the recruitment rates and successful enrollment into the study
- To assess the % of infants with measurable TV and successful adjustment of PiP to reach goal TV
- To assess the % of infants who fail VTV and need to be switched to conventional PLV

Specific Aims #2: To compare the pulmonary mechanics and physiology during VTV, respiratory support requirements

Objectives:

- To compare TV delivered during PLV versus VTV.
- To compare FiO2 requirement during PLV versus VTV
- Evaluate PiP, mean airway pressures (Paw), peak end expiratory pressures (PEEP) and oxygen requirement during the first 48 hours between the two study arms.
- Evaluate differences in blood gas results (pH, PCO2 levels).

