Specific Aim #3: To assess complication rates and long term outcomes for infants receiving VTV versus PLV.

Objectives:

- To compare the total duration of neonatal resuscitation before reaching a stable state ready for transfer to NICU from the DR
- To record APGAR scores as a means to evaluate the ongoing resuscitation
- Compare oxygen requirements between VTV and PLV group during DR resuscitation
- To assess the incidence of complications including pneumothorax
- To evaluate for other unexpected adverse events that may be associated with VTV
- Evaluate longer term pulmonary morbidities: duration of invasive ventilation, BPD rates, and home oxygen requirements at discharge.

DESIGN AND PROCEDURE

EXPERIMENTAL DESIGN

Phase I: Phase I will be an observational, non-interventional study. All infants will receive routine resuscitation as recommended by the NRP. A flow sensor device connected to Respironics NM3 monitor (*Philips Healthcare, Eindhoven, Netherlands*), will be placed between the ETT and T-piece resuscitator to measure breath to breath tidal volume. Providers will be blinded from the actual TV measurements as in routine clinical scenario, and no intervention will be recommended or planned based on the TV measurements.

We will select a convenience sample of 10 patients. All preterm infants born < 32 weeks at Baystate Medical during the 1 year study period will be screened for possible inclusion.

Phase II: We will conduct a randomized control trial to assess feasibility of VTV in the delivery room compared to PLV in preterm infants.

SELECTION OF SUBJECTS

All preterm infants born < 32 weeks at Baystate Medical Center during the 1 year study period will be screened for possible inclusion. With annual delivery of approx.4000 infants, of which 80-100 infant born < 32 weeks gestation, there will be sufficient patient population for the proposed pilot study.

Inclusion Criteria:

- Gestational age < 32 weeks of gestation
- Infant born at Baystate Medical Center
- Requiring intubation and positive pressure ventilation in the delivery room
- Parental Consent

Exclusion criteria:

- Maternal prolonged rupture of membrane > 2 weeks duration
- Known congenital or cardiac abnormalities or discovered in the immediate neonatal period.

Withdrawal/Termination Criteria:

- Withdrawal of parental consent

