PHASE I: No specific withdrawal/termination criteria will be required as this is an observational study to assess feasibility of measuring tidal volume in the DR. Infant will continue to receive routine care as recommended by NRP, even if TV measurements are unsuccessful.

PHASE II: Control Arm: No specific withdrawal/termination criteria will be required, as these infant will continue to receive routine care per NRP recommendations without any study related intervention.

Intervention Arm: If TV cannot be measured or VTV cannot be provided within 60 seconds of initiating PPV via the ETT, the infant will be automatically switched to receiving routine care as recommended by the NRP.

INFORMED CONSENT PROCESS AND TIMING

Who: Parent.

When: "Deferred consent" is being requested after the birth of the child. The study process starts as soon as the baby is born and requires intubation as determined by the clinical team providing resuscitation. We will obtain a deferred consent from the parents only if the baby requires intubation in the delivery room and the TV measurements were obtained. We will approach the parents to use the data that was collected in the delivery room.

Rationale for deferred consent: *In an ideal situation, the consent should be obtained prior to study intervention. However, since the study intervention starts within few seconds to minutes of the baby's birth and it is not*

possible to determine which baby will need intubation in the delivery room, it would be unrealistic to have the opportunity to obtain informed consent we will aim for "deferred consent" process. As this study only present minimal risk to the infants and the device being used is an FDA approved device for use in neonates, a deferred consent is being requested for from the IRB.

How much time to decide: Since study related interventions has already occurred and we are asking parents to give consent for using this information as well as review of electronic medical records parents will have adequate time to make this decision free of any coercion to participate in the study.

Person authorized to obtaining consent: All investigators, program coordinator associated with the study.

SUBJECT FEES: None

REIMBURSEMENT/RENUMERATION FOR PARTICIPTION: None

RISK BENEFIT ASSESSMENT

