Providing VTV to the VLBW infants is a standard of care practice upon admission to the NICU, with this study we seek to provide more physiologic VTV to the infant immediately after birth without any delay.

Phase I: No risk and no benefit directly to the patient, as this is the observational phase of the study. Information obtained from this phase study may potentially be beneficial by supporting the need for future studies in preterm infants with need for invasive respiratory support.

Phase II: Infants in intervention arm will receive the same routine care with additional information about the TV being delivered to the study infants. The provider's ability to adjust the PiP to provide goal TV may be potentially beneficial for the study infants, as in current DR practice the delivered tidal volume is unknown and infant may be receiving TV out of the set goal range. Infants in the control arm will not have any direct risk or benefit. The only concern would be adding less than 1ml of dead space with the flow sensor, which may or may not be of any clinical significance at all.

UNANTICIPATED PROBLEMS AND SERIOUS ADVERSE EVENT REPORTING

Unanticipated problems and serious adverse events to the subjects related to the study will be reported to the IRB within 48 hours of the occurrence.

RANDOMIZATION

Phase I: No randomization. All infants will receive pressure regulated breaths, 40-60 breaths/min, PiP of 20-24cm of H₂O as recommended by 2017 Neonatal Resuscitation Program (NRP) guidelines. Providers will be blinded from the measured TV during the resuscitation.

Phase II: All infants born <32 weeks will be randomized to one of the study group. Randomization will be via sealed envelope, opened in DR after the decision to intubate is made, with a 1:1 randomization ratio. To keep the gestational age in the two study arm relatively similar, as we are proposing only a small sample size for this current study, randomization will be stratified by gestation age group (Randomization subgroup I: <28 weeks and subgroup II: 28-32 weeks). Infants in both the arms will have a flow sensor at the ETT connected to Respironics NM3 monitor (Philips Healthcare, Eindhoven, Netherlands), to measure breath to breath TV.

INTERVENTION

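### Phase II does not say that infants switched from VTV to PLV are analysed in their assigned arm; on the as-received wording, FiO2, complication and BPD estimates could be biased in favour of VTV

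*Combined protocol and SAP*

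**What the plan says.** **The switch.** Under Withdrawal/Termination Criteria (Selection of Subjects), failure to measure tidal volume or to give VTV within 60 seconds of starting PPV through the tube has this consequence in the intervention arm: "the infant will be automatically switched to receiving routine care as recommended by the NRP". According to the Intervention section, that care is pressure-limited ventilation, the control treatment. For controls the same place reads "Control Arm: No specific withdrawal/termination criteria will be required".

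**Comparisons worded by ventilation received.** An objective of Phase II Aim 2 is "To compare FiO2 requirement during PLV versus VTV", and the tidal volume objective is worded in the same way. Aim 3 is "To assess complication rates and long term outcomes for infants receiving VTV versus PLV".

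**Comparisons worded by arm or group.** Another Aim 2 objective sets PiP, mean airway pressure, PEEP and oxygen need over 48 hours against each other by study arm. One Aim 3 objective, and the Data Analysis text on ventilatory measures and BPD trends, speak of groups without saying whether these are assigned or received.

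**Follow-up.** Study Endpoints keeps the infant in the randomised arm for 48 hours with data collection, which then continues for longer-term outcomes. Aim 1 already counts infants who fail VTV and are switched.

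**Consent.** Informed Consent Process and Timing seeks deferred consent only where tidal volume measurements were obtained. Vulnerable Population requires written consent before any Phase II intervention.

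**The concern.** Crossover runs one way, from VTV to PLV, and no analysis population is defined. Oxygen need shows the difficulty: the aims compare it by ventilation received in one line, by study arm in another and by group in a third. A switched infant belongs to a different side depending on which line the analyst follows.

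Failure of VTV is unlikely to be random. Potential Pitfalls and Alternatives foresees that the monitor may not register the very small volumes of extremely low birth weight infants. The subject stopping rules add persistent low saturation or bradycardia on VTV. If these infants leave the VTV group, that group keeps the better-prognosis infants. If they are added to PLV, the contrast widens further.

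Phase II will produce point estimates, and Data Analysis says they will supply effect sizes and variability for a later trial. An effect inflated in this way would make that trial too small. Providers are also unblinded, so the choice of comparison should not be left until the data are in hand.

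**Working it through.** **1. The plan's own figure.** The sample size is stated as "We will enroll a total of 30 patients (15 per study group", allocated "with a 1:1 randomization ratio". The precision claim is "with 30 patients, the width of the 95% confidence will be about 55% as wide as the standard deviation". A chi-square 95% interval for an SD with n = 30 runs from 0.796 to 1.344 SD, a width of 0.548, so the 55% is reproduced. (A t half-width for a mean with n = 15, 0.554 SD, also fits.) The figure concerns precision and is unaffected by this point.

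**2. Bias with no true effect.** Inputs: 15 per arm (Sample Size); m infants switched; prognostic shift d, in SD units, between infants in whom VTV fails or would fail and the rest, with the same share m/15 of such infants in both arms. The documents give neither m nor d. The base case m = 3 borrows the 20% shortfall that the Phase I feasibility definition tolerates. Both m and d are assumptions. Higher values are worse, so a negative difference (VTV minus PLV) favours VTV.

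- Counted as PLV: the VTV mean is 0 and the PLV mean is (m·d + m·d)/(15 + m), so the difference is -2·m·d/(15 + m).
- Excluded: the VTV mean is 0 and the PLV mean is m·d/15, so the difference is -m·d/15.
- By randomised arm: both means are m·d/15, so the difference is 0.

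| m of 15 | d | Counted as PLV | Excluded | By randomised arm |
|---|---|---|---|---|
| 1 | 1 | -0.125 | -0.067 | 0 |
| 3 | 0 | 0 | 0 | 0 |
| 3 | 0.5 | -0.167 | -0.10 | 0 |
| 3 | 1 | -0.333 | -0.20 | 0 |
| 5 | 0.5 | -0.25 | -0.167 | 0 |
| 5 | 1 | -0.50 | -0.333 | 0 |

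**3. Cross-check.** Let failure be the worst 20% on a normal severity scale that correlates 0.5 with outcome. The normal density at the cut-off is 0.280. The remaining infants average -0.5 × 0.280/0.8 = -0.175 and the switched infants 0.5 × 0.280/0.2 = 0.700, which implies d = 0.875. The differences are -0.175 if excluded and -0.175 - (3 × 0.700)/18 = -0.292 if counted as PLV. In 20,000 simulated trials without a true effect, each infant failing with probability 20%, VTV looked better in about 79% if switched infants counted as PLV, 68% if excluded and 50% by randomised arm.

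**4. BPD.** Take 40% in both arms. The protocol gives this for 28 weeks or less; applying it to all infants is an assumption. With 3 switched at an assumed 80% risk, the remaining 12 have (6 - 2.4)/12 = 30%, and PLV including the switched has (6 + 2.4)/18 = 46.7%. The difference is -16.7 points if counted as PLV, -10 points if excluded (30% against 40%) and 0 by randomised arm. At 60% risk the first two are -8.3 and -5 points; at 40% both are 0.

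**5. Will any switch occur?** The chance of at least one among 15 is 1 - (1 - p)^15: 96% at p = 20%, 79% at 10%, 54% at 5%.

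**6. Primary outcome.** Phase II asks whether VTV starts at a time similar to PLV. An infant switched at 60 seconds has no VTV start time. Leaving such infants out would cap the VTV times at 60 seconds.

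**The case against.** The strongest reply is that no section declares an as-received analysis. Part of Aim 2, including PiP, is by study arm; the Randomization section uses group for the assigned arm; and Study Endpoints keeps infants in their randomised arm with continued data collection. A reader might infer that the plan removes switched infants or moves them to PLV. The documents do not go that far: the rule switches care and does not say that data or analysis membership changes. What stands is that the rule sits under a withdrawal heading, several objectives are worded by receipt, and nothing resolves the conflict.

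A reader might also infer that only VTV infants can be withdrawn. That is too broad. Consent withdrawal applies to both arms, and the pneumothorax/pneumomediastinum and PiP stopping rules name no arm. Only the 60-second switch is clearly one-sided. The consent condition about obtained measurements is not arm-specific either.

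Nor do the documents show that VTV will look better. A failure can be logistical, such as equipment not being ready, and for a large leak the protocol has a fallback to expiratory volume. If failure is unrelated to prognosis, the bias is zero.

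Finally, "no formal tests of hypotheses will be conducted", and with 15 per arm the standard error of a mean difference is √(2/15) = 0.37 SD, so the base-case biases lie within one standard error. That limits what one would conclude from this pilot alone. It does not protect the effect sizes passed to the next trial, since the error is systematic.

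**Conclusion.** The point holds as a conditional one and should be settled before Phase II starts. The analysis set is undefined, the wording is mixed, and two of the available readings take failed-VTV infants out of the VTV group. The direction, in favour of VTV, rests on the protocol's expectation of measurement failure in the smallest infants; the size rests on an assumed switch rate and prognostic shift. With 3 of 15 switched and a shift of 0 to 1 SD, the spurious difference is 0 to -0.33 SD if they are counted as PLV and 0 to -0.20 SD if excluded. Analysis by randomised arm removes this bias whatever the switch rate or shift. The outcomes exposed are FiO2, complications and BPD, plus the primary timing outcome for lack of a rule. The PiP objective is already by study arm.

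**What to change.** - State in Data Analysis that all Phase II comparisons, including the primary timing outcome, use all randomised infants by assigned arm. Give the timing outcome a rule for infants who never start VTV, for example counting them as not started within 60 seconds.
- Reword the Aim 2 and Aim 3 lines that refer to ventilation received so that they refer to the randomised arms, and define group in the same way.
- Keep switched infants in their assigned arm, with the data collection that Study Endpoints already plans to 48 hours and for longer-term outcomes.
- Under Aim 1, report the number of switches and the reason for each. Label any summary restricted to time on VTV as supplementary.
- Reconcile the withdrawal heading with Study Endpoints. Reconcile the consent text, which seeks deferred consent only where measurements were obtained, with the requirement in Vulnerable Population for prior written consent and with the need to keep data from infants whose measurement failed.

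The analysis changes cost a few sentences. The sample size stays at 30, and the data come from collection already planned, provided the consent text permits their use. No change to the clinical switching rule is proposed.
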